### **Exercise Lab Space**

The exercise classes and cognitive training will be held in the Movement Studies Laboratory in the Atlanta VA Rehab R&D Center. The Movement Studies Laboratory is a 41 X 34 ft. work out area that will serve as the venue for the group exercise. Because the lab space is housed in the Atlanta VAHCS, emergency procedures are done in accordance with emergency preparedness plans. A phone is located in the facility which can be used to contact emergency services (911) in the event of a medical emergency. CPR and the AED will be utilized if needed until Emergency Services assumes responsibility. All staff are certified in basic life support and first aid and the facility houses AED devices. A second location for exercise classes is the Geriatric Research

Education and Clinical Center (the GRECC), an offsite Atlanta VA affiliate facility, that follows the same rules and regulations as the rest of the Atlanta VA Healthcare System.

## **Risks/Discomforts**

### *Cognitive Testing*

Patients may experience some frustration if they have trouble with cognitive testing. Researchers will be trained on how to handle frustration by taking breaks, allowing patients to express frustration, and offering encouragement. As noted above, we will also include items that the participants can answer correctly to minimize frustration. In the vast majority of patients, these techniques are adequate to deal with frustrations.

### *Magnetic Resonance Imaging (MRI)*

More than 150 million diagnostic magnetic resonance studies have been performed worldwide. The vast majority of these procedures were completed with no sign of patient injury. There is a high degree of patient safety with an fMRI because of the miniscule value of magnetic susceptibility and lack of ferromagnetic components of human tissue. Studies have ranged in magnetic field intensities from 1.5 to 8T. No negative cardiac, physiological, or cognitive effects were noted. Therefore, long-term effects on human health from magnetic resonance imaging are unlikely. Those at risk for injury include those with indwelling ferromagnetic material (e.g. foreign object in eye, surgical implant) or an implanted bioengineering device (e.g. pacemaker, infusion pump), due to the possible interaction with a magnetic field. Subjects identified as at risk from the screening checklist will be excluded from the study.

Another potential hazardous effect is related to the high-level of noise produced by the machinery during imaging. Unprotected, patients can experience hearing loss. For this reason, individuals will be given foam earplugs to wear to minimize this risk.

Additionally, some individuals are perceptible to experiencing distress during the fMRI process. The small, closed-in space may trigger anxiety. Participants will be screened for claustrophobia, generalized anxiety disorder, post-traumatic stress disorder, or obsessive-compulsive disorder.

Further, persons who are pregnant (or could be pregnant) or those with a seizure disorder should not undergo magnetic resonance imaging and will be excluded.

The reported potential side effects of the CO2 mask may include a feeling of dizziness, faintness, or anxiety during CO2 inhalation.

Subjects may have early stages of disease, not previously diagnosed, detected through the use of MRI. A trained neuroradiologist is available to the investigators to evaluate the findings and determine if there is pathology present or a normal variant should the investigators suspect that the imaging shows abnormalities. If pathology is present or suspected, subjects will be counseled about what the findings are and what should be the next steps for clarification of ambiguous findings or seeking help with pathological

findings. This is not a risk in the conventional sense of physical harm or disease but does pose a potential psychological risk to the patient.

### *Blood Draw*

The risks of drawing blood from a vein include discomfort at the site of injection; possible bruising and swelling around the injection site; rarely an infection; and, uncommonly fainting from the procedure. A trained phlebotomist will collect all blood samples following standard protocol.

### *Physical function and Exercise Intervention*

While the risk of a cardiac emergency is increased when a person is exercising, these events are rare and usually occur during high-intensity activities. The cardiovascular benefits of exercise have been consistently shown to outweigh the acute cardiovascular risk during the act of exercising. Moreover, a person beginning a moderately intense exercise program is actually at a lower overall risk of sudden death than their sedentary peer. Neither an ECG nor a stress electrocardiogram will be included in the screening process due to the lack of evidence to support their usage in detecting those who will have an adverse exercise outcome.

Some participants will experience exercise-related injuries and possibly muscle soreness and fatigue as a result of the testing and the intervention. There is a small risk for loss of balance and injury from a fall while walking and during balance measurements. However, walking and balance measurements will only be a few minutes at a time, and research personnel will be with the participant at all times. Most injuries will be self-limited, though it is possible for permanent injuries to occur, including broken bones or joint problems. There are minor risks of musculoskeletal problems associated with the performance evaluation measures of the study.

The potential risks of loss of confidentiality will be minimized through assigning all data collection instruments a unique code without individual identifying information. All HIPAA regulations pertaining to protection of participants and eliminating identification will be followed.

### **Potential Benefits**

There are substantial potential benefits of participation in this study. All participants may benefit from the pre-intervention evaluation, which may detect unknown or inadequately treated medical problems. Potential benefits for adults who exercise include:

- improvement of physiologic indicators of health (e.g., balance, blood pressure);
- full or partial elimination of impairments in ability to do daily activities;
- improvement in mental and/or social health status;
- reduction of risk of falls and fall-related injuries; reduction in risk of mortality; and reduction in medical care costs.

Potential benefits for adults who participate in the exercise testing include:

- improved awareness of their cardiovascular fitness level;
- greater confidence in the knowledge of their cardiovascular fitness level;
- greater knowledge of their fitness changes and the relationship between those measures and their ADLs.
- improvement in mental and/or social health status;
- reduction of risk of falls and fall-related injuries;
- reduction in risk of mortality; and
- reduction in medical care costs

## **6. Participant selection:**

The study will enroll sedentary older adults and young adults as a comparison group for the MRI scans. Older adult participants will be pseudo-randomized to one of three 12week intervention conditions: Aerobic Exercise, Interval Exercise, or Control. The pre and post evaluations will be conducted over 2 days during a 1-week period. Each day will last no more than 2 hours. The investigators expect a dropout rate of anywhere from 15-20% of participants. To ensure completion of study by 108 participants, as many as 134 subjects may be enrolled.

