#### **4. Specific Aims:**

The study will enroll 134 older, sedentary adults. Participants will be pseudorandomized to one of two 12-week intervention conditions: Aerobic Exercise or Stretching.

**Specific Aim 1:** To determine the effect of a 12-week aerobic exercise intervention on changes in cerebral perfusion using arterial spin labeling in older Veterans.

*Hypothesis:* Compared to a non-aerobic intervention Control group, the aerobically trained group will have increased basal perfusion in areas that demonstrate age-related decline and are malleable to aerobic exercise (inferior frontal and motor cortices).

**Specific Aim 2:** To determine the effect of a 12-week aerobic exercise intervention on changes in cerebrovascular reactivity using a hypercapnic CO2 response test in older Veterans.

*Hypothesis:* Following the interventions, aerobically-trained older adults will have increased CVR to CO2 in the inferior frontal and motor cortices when compared to controls.

**Specific Aim 3:** To quantify the impact of cerebrovascular perfusion and cerebrovascular reactivity on the BOLD response during task-based (cognitive executive and motor) fMRI.

*Hypothesis:* Perfusion and CVR will account for a significant portion of variability in the BOLD response during task-based fMRI both before and after the intervention.

*Measures for Specific Aim 3.*

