### Blood Draws and Biomarker Evaluation

Whole blood will be collected, by a certified phlebotomist, through one venous port venipuncture or peripheral venous line into standard plasma tubes or serum separator tubes (~40 ml per visit). Following collection, tubes will be transferred in accordance with blood borne pathogens training standards to the Molecular Core facility of the Atlanta VAHCS. Serum and plasma aliquots will be analyzed for biomarkers (e.g., BDNF) by ELISA, western immunoblotting, and other standard molecular biology assays.

Saliva will be collected at study assessment visits in a 15mL sterilized tube; roughly 3mL. Once collected, saliva will be immediately placed on ice and stored at -80 degrees until subsequent analysis.

The procedure below describes the blood and saliva collection timeline during the 12-week intervention period for both intervention groups:

*Week 1:* Taken immediately prior to exercise, immediately post, 15 min post, 30 min post.

*Week 6:* Taken immediately prior to exercise, immediately post, 15 min post, 30 min post.

*Week 12:* Taken immediately prior to exercise, immediately post, 15 min post, 30 min post.

All blood draws will be conducted at the Atlanta VA Health Care System. Tubes will be coded and thus have no identifiable patient information. It is expected that all blood sample processing and storing will be conducted at the Atlanta VAHCS in the Molecular Core facility. However, in the event that equipment or other resources are needed for completing sample analysis, samples will be analyzed at Emory University (5th Floor, Emory Eye Center, Clinic Building B, [name]). Sample labels will be de-identified by having only Subject #, Visit #, Draw #. The master code list will be maintained in a locked file cabinet in the Atlanta VAHCS office of the PI or Coinvestigator. Deidentified sample remainders will be kept at the Atlanta VA Core facility or, if needed, the Emory facility, while the study remains open.

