#### **Interventions**

*Aerobic Exercise Group:* For this arm of intervention, randomized participants will attend spin exercise training sessions demonstrated to facilitate physiological changes. For the

aerobic exercise component of this group, participants will follow the guidelines provided by the American College of Sports Medicine for optimizing cardiovascular fitness. Thus, participants will exercise 3 times a week on a stationary ergometer. Exercise intensity will begin at low levels (50% of maximal heart rate reserve) calculated utilizing the Karvonen method. Briefly, target exercise HR is calculated by subtracting the persons age from 220. Resting heart rate is then subtracted from this number. The answer is then multiplied by the target percent (50% for example) and the product is added back to resting heart rate to provide the target exercise session heart rate. Intensity will be increased by 5% every week (as tolerated by the participant) to a maximum of 90% of maximal heart rate. Exercise time will progress from an initial 25 minutes per session to a maximum of 60 minutes by increasing 5 minutes each week. Each session will be monitored by a certified CPR and fitness specialist. Further, the intervention site is located in the Atlanta VA Health Care System and portable defibrillators are available at the intervention site.

*Interval Exercise Group:* For 12-weeks participants will engage in progressive whole body stretching, toning and balance exercises designed for individuals 65 years and older. Participants will meet for the same total duration time as the aerobic exercise group. Heart rate will be monitored to ensure participants maintain exercise levels below aerobic training zone.

*Remote Exercise Monitoring:* As an alternative, participants that are uncomfortable with receiving face-to-face training within the hospital will be given the option to continue their exercise intervention visits remotely. For participants that have been randomly assigned to the 'spin' exercise training program, will be provided a stationary cycle ergometer that has been sanitized properly to use during the 12-week period. All subjects will be monitored and trained through VA and Emory approved remote access sites.

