*Control Group:* A random subset of participants will be in a 12-week wait-list control. These participants will undergo the same scanning procedures as described above without cognitive or physical function testing. After 12-weeks these participants will come in and undergo the pre-assessment, 12-week exercise intervention and post assessment as described above.

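### The plan describes a two-arm and a three-arm trial and uses Control for two different groups, so the Aims 1 and 2 comparator is ambiguous and 44 per group cannot be confirmed

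*Combined protocol and SAP*

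**What the plan says.** **Arms.** Section 4 (Specific Aims) states "The study will enroll 134 older, sedentary adults" and then "Participants will be pseudorandomized to one of two 12-week intervention conditions: Aerobic Exercise or Stretching". Section 6 (Participant selection) states "Older adult participants will be pseudo-randomized to one of three 12week intervention conditions: Aerobic Exercise, Interval Exercise, or Control", and also enrols young adults as an imaging comparison group, with no number given.

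**Labels.** The Aim 1 hypothesis in section 4 reads "Compared to a non-aerobic intervention Control group, the aerobically trained group will have increased basal perfusion". In section 5, under Interventions, the arm headed Interval Exercise is one in which "participants will engage in progressive whole body stretching, toning and balance exercises", so its content is that of the stretching arm in section 4. The next heading, Control Group, says "A random subset of participants will be in a 12-week wait-list control". Those participants have the same scans, without cognitive or physical function testing, and are later assessed and given the exercise intervention.

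**Analysis.** In section 7, the analyses for Aims 1 and 2 compare two groups, Spin and Control. Neither defines Control, and no analysis is described for a third condition.

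**Numbers.** Section 6 plans up to 134 enrolled for 108 completers at 15-20% dropout. The power section uses 44 per group and 88 subjects.

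**The concern.** The comparator decides what Aims 1 and 2 estimate. Of the stretching arm the plan says "Participants will meet for the same total duration time as the aerobic exercise group", so a contrast with it separates aerobic training from contact and attendance, as the Aim 1 hypothesis intends. A contrast with the wait-list estimates aerobic training together with contact and attendance.

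If the labels of section 6 and the Interventions section are carried into section 7, Control is the wait-list and the analysis does not test the stated hypothesis. If the label of section 4 is carried forward, Control is the stretching arm. Perfusion and CVR would be measured in both groups, so either contrast could be reported under the same words, and the wording leaves room to choose after the data are seen.

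The count has the same weakness. Section 4 makes all 134 older adults. Section 6 speaks of up to 134 subjects after introducing young adults, and its eligibility criteria put ages 18 to 80 in the final pool. The detectable effects in the power section cannot be checked until the number per arm is known.

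**Working it through.** **1. The enrolment figure.** Enrolment = completers / (1 - dropout). 108/0.85 = 127.1, so 128; 108/0.80 = 135. The stated 134 implies dropout of 1 - 108/134 = 19.4%, so 134 and 108 agree with each other.

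**2. Does 44 per group follow?** Equal allocation is my assumption, since no ratio is stated.
- Two arms: 108/2 = 54 completers each.
- Three arms: 108/3 = 36 each.
- 44 in each of two analysed arms: 108 - 88 = 20 left for a third group or young adults. This is possible but not stated.
- Working back from 44 completers per arm at 15-20% dropout: two arms (88) need 104 to 110 enrolled; three arms (132) need 156 to 165. Neither is 134.
- 134/3 = 44.7 is close to 44, but that counts participants before dropout.

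If young adults count within the 108, every figure for older adults falls.

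**3. Power at each candidate size.** The effect sizes and alphas are the plan's; two-sided testing is assumed because the plan does not state it.

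*Between-group fluency*, d = 0.64, stated power 0.80. Two-sample noncentral t with df = 2n - 2 and noncentrality d x sqrt(n/2). At n = 44 this is 0.64 x sqrt(22) = 3.00, against critical values of 2.264 (alpha 0.0261) and 1.988 (alpha 0.05). The plan prints an alpha of .05 described as FDR-corrected but uses 0.0261 elsewhere, so both are shown.

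| n per arm | Power, alpha 0.0261 | Power, alpha 0.05 | Detectable d at 0.80 (0.0261 / 0.05) |
|---|---|---|---|
| 54 | 0.86 | 0.91 | 0.597 / 0.544 |
| 44 (plan) | 0.77 | 0.84 | 0.663 / 0.604 |
| 36 | 0.67 | 0.76 | 0.736 / 0.670 |

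Power of 0.80 needs 48 per arm at alpha 0.0261, or 40 at 0.05.

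*Within-Spin change*, d = 0.5, alpha 0.0261, stated power 0.80. One-sample noncentral t with noncentrality d x sqrt(n): power 0.91 at n = 54, 0.84 at 44, 0.75 at 36. Detectable d is 0.43, 0.48 and 0.53. The plan's statement holds at 44 and 54 and falls slightly short at 36.

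*Aim 1 at the plan's halved effect*, d = 1.37, alpha 0.0261: power exceeds 0.99 at all three sizes, whether treated as within-group change or as a two-group contrast.

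*Aim 3*, noncentral F, three model terms tested together, alpha 0.05, power 0.80: detectable R2 is 0.115 at N = 88 (the plan states 0.111, for which I get power 0.78), 0.095 at N = 108, and 0.138 at N = 72. The last assumes that only two arms of 36 enter the regression.

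**4. Which group is Control?**

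| Points to stretching | Points to the wait-list |
|---|---|
| Aim 1 hypothesis: a non-aerobic intervention group | Interventions: the wait-list carries the heading Control Group |
| Blood Draws: "timeline during the 12-week intervention period for both intervention groups" | Section 6: Control is listed separately from Interval Exercise |
| Aim 1 analysis: speaks of interventions in the plural | |
| Power section: plans a between-group fluency contrast, but the wait-list has no cognitive testing in its control period | |

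Stretching is the more likely intent. The labels in force say otherwise, and no sentence resolves the conflict.

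**The case against.** The strongest reply is that the comparator is clear in substance. The only stated Aim 1 hypothesis names a non-aerobic intervention group, a wait-list is not an intervention during its waiting period, and most of the surrounding text speaks of two intervention groups. On that view the rest is loose labelling. This stands as a reading of intent. It does not remove the conflict, because section 6 makes Control a randomised condition distinct from the stretching arm, and the analysis section uses that same word.

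A second reply is that 36 per arm does not follow even from three conditions. Wait-list participants later receive assessment and the exercise intervention, so they could rejoin the arms; an even split would restore 54. That is also fair, though the plan does not say they would be analysed that way. Likewise, N = 72 for Aim 3 holds only if the wait-list is left out of the regression, which the plan does not say.

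A third reply is that power for Aim 1, on which the study is mainly sized, barely moves. That is correct. The visible drops concern semantic fluency, a behavioural outcome, and the 0.77 at 44 per arm comes from the choice of alpha, not from the number of arms. Nor do the documents show that anyone intends to choose the comparator after seeing data; they only leave that open.

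**Conclusion.** The concern holds. Sections 4 and 6 describe incompatible designs for the same older adults, and Control names two groups that would both be scanned and would give different estimates for Aims 1 and 2. This must be fixed because the main contrast is not uniquely defined; loss of power is not the reason. The figure of 44 per group is neither confirmed nor refuted. Under assumed equal allocation of 108 completers it could be 54 or 36, which moves power for the between-group fluency effect between 0.86 and 0.67 at alpha 0.0261 (0.91 and 0.76 at alpha 0.05). A shortfall is not proven. Confidence is high on the arms, labels, comparator and counts; the 36-per-arm and N = 72 figures are scenarios only.

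**What to change.** Reconcile sections 4, 5 (Interventions), 6 and 7 to one design with one label per arm. Specifically:

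- Name the stretching and toning arm as the comparator for Aims 1 and 2, in line with the stated hypothesis, and use that name in the analysis section.
- Say whether the wait-list is a randomised third condition or a delayed-start subset, and whether its data enter any analysis.
- Give the allocation ratio, and the number randomised and expected to complete in each arm.
- State whether wait-list and young-adult participants count toward the 134 and the 108.
- Restate the between-group detectable effect, with the alpha and sidedness used, and the Aim 3 R2, at the actual numbers.

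This is protocol amendment text and adds no participants. The one cost is that the stated detectable effects may become less favourable if the actual number per arm is below 44.

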### **Inclusion/Exclusion Criteria**

Prior to beginning any portion of this study, we must receive a physician, physician assistant, or nurse practitioner's written medical approval for participation in the fitness assessment and/or exercise intervention. We will provide a letter to sign explaining the study protocol. The key inclusion criteria and final participant pool will consist of right-handed English-speaking individuals ages 18 to 80. Older participants will be sedentary as defined by <40 min/week of aerobic exercise. Additionally, participants will be non-demented and will have no cognitive-executive function deficit (MoCA  $\geq$  26). Further, those with severe diabetes requiring insulin will also be excluded. However, those with less severe, controlled diabetes that meet our physical and cognitive function inclusion criteria will be allowed to participant. Participants must not have conditions incompatible with MRI (including but not limited to, ferrous metal implants, cardiac pacemakers or similar devices, claustrophobia, morbid obesity). Potential participants with major psychiatric disorder (including but not limited to psychosis, major depression, bipolar disorder) by history will be excluded.

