### **Recruitment**

Individuals will be recruited from the Atlanta VA Rehab R&D Subject Registry (IRB00000159) based on the inclusion and exclusion criteria. The Subject Registry study staff will query the database of all patients meeting the inclusion and exclusion criteria who have consented to be contacted for research purposes and will print out their contact information. The Principal Investigator, or his research colleagues, will contact these individuals and will summarize the study procedures. If the potential participant is interested, we will mail them a copy of the informed consent and will

schedule an orientation session that describes the study goals and provides an opportunity to go over the informed consent.

In order to decrease burden of the potential recruitment pool of participants, cognitive, motor, and physical function measurements will be shared between this study Effects of Acute Exercise on Functional Magnetic Resonance Spectroscopy Measures of GABA in Aging and Chronic Stroke (IRB00001334) and Graded Intensity Aerobic Exercise to Improve Cerebrovascular Function and Performance in Aged Veterans (IRB00106626) as all studies administer the same assessments.

Healthy subjects will also be recruited via the Emory University Alzheimer Disease Research Center (ADRC) Registry. Written permission from all patients is recorded on a signed informed consent form before inclusion in the ADRC Registry. This consent requires that the patients be willing to complete detailed histories, undergo comprehensive neurological and neuropsychological evaluations on an annual basis; submit blood for ascertainment of genetic information and establishment of lymphoblastoid cell lines; and agree to be contacted regarding participation in research projects of Emory investigators.

CDW/VINCI data will be used to identify potential research participants. Veterans who are age 65 or older and who live within 20 miles of the Atlanta VA Health Care System will be identified and contacted via mail and then subsequently by phone. Addresses and phone numbers will be used for recruitment only and the information will be verified as current and accurate in CPRS prior to use.

Additionally, participants may be recruited from word of mouth, newspaper advertisement, and study flyer distribution within the Atlanta VA Health Care System and surrounding community.

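### The Aim 3 regression of task BOLD on perfusion and CVR has no age term, and 'older' has no lower age limit, so age differences between participants can create or inflate the association.

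*Combined protocol and SAP*

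**What the plan says.** **The model.** Section 7, Statistical Analysis for Specific Aim 3, regresses task BOLD in each region of interest on CBF, CVR and CBF × CVR, for the pre and post sessions. There is no age term and no stated analysis set. Age appears only in the additional regressions for Aims 1 and 2.

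**Age and the predictors.** Section 3 reports that, in the investigators' own data, older adults have lower perfusion than younger adults in the inferior frontal gyrus and motor cortex, which are the regions named in Aims 1 and 2. It also reports that CVR falls markedly with age in their pilot data.

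**Who is eligible.** Inclusion/Exclusion Criteria gives a single age range: the "final participant pool will consist of right-handed English-speaking individuals ages 18 to 80. Older participants will be sedentary". The sentence goes on to define sedentary by weekly exercise time, not by age. Section 6 adds: "Older adult participants will be pseudo-randomized to one of three 12week intervention conditions". So the word 'older' decides who is randomised, but it has no number attached.

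**Where 65 appears.** As a filter on one recruitment route ("Veterans who are age 65 or older and who live within 20 miles"), as a description of the comparison programme ("stretching, toning and balance exercises designed for individuals 65 years and older"), and in background figures. It is not an eligibility criterion.

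**Who makes up the 134.** Section 4: "The study will enroll 134 older, sedentary adults". Section 6: "The study will enroll sedentary older adults and young adults as a comparison group for the MRI scans", followed by the same total of 134 for subjects in general.

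**The concern.** Aim 3 compares people with one another; it does not use the randomisation. Anything that shifts CBF or CVR and also shifts task BOLD can therefore appear as a CBF or CVR effect. Age is the obvious candidate, because the plan itself says it moves both predictors in the regions under study.

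The wider the age range, the larger this effect. The registry, research-centre, newspaper, flyer and word-of-mouth routes add no lower age of their own. A sedentary volunteer of 50 breaks no written age rule, and staff must decide whether that person is older.

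At stake is the Aim 3 conclusion that perfusion and CVR account for a meaningful share of BOLD variance. That share could partly be a share explained by age.

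**Working it through.** **1. The plan's own Aim 3 figure.** Power Analysis and Sample Size gives 88 subjects, α = .05, power 0.80 and a detectable R² increase of 0.111. For the overall F test with 3 predictors, the noncentrality is λ = N·R²/(1 − R²) = 88 × 0.111/0.889 = 10.99, on 3 and 84 degrees of freedom. Power is 0.783, and the smallest R² with 80% power is 0.115. The figure reproduces closely and is not disputed.

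**2. Assumptions for the age effect.** The documents give no correlation of age with regional CBF, CVR or task BOLD, so these are assumed:
- ages are uniform over the range;
- CBF, CVR and BOLD each have the same correlation ρ with age within 65-80, taken as 0.1, 0.2 or 0.3;
- the slope on age and the residual SD stay the same when the range widens;
- given age, BOLD has no relation to CBF or CVR.

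**3. Correlation with age over a wider range.** For a range of width w years, s = (w/15)·ρ/√(1 − ρ²) and r = s/√(1 + s²). For ages 50-80 and ρ = 0.2: s = 2 × 0.2/0.980 = 0.408, so r = 0.408/√1.167 = 0.378. For ρ = 0.1 and 0.3, r is 0.197 and 0.532.

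**4. R² produced by age alone.** CBF and CVR each correlate r² with BOLD and r² with each other, so the population R² of the two together is 2r⁴/(1 + r²).
- Ages 65-80, ρ = 0.2: 2 × 0.0016/1.04 = 0.003.
- Ages 65-80, ρ = 0.3: 2 × 0.0081/1.09 = 0.015.
- Ages 50-80, ρ = 0.2: 2 × 0.0204/1.143 = 0.036.
- Ages 50-80, ρ = 0.3: 2 × 0.0801/1.283 = 0.125, above the plan's 0.111.

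**5. Rejection rate of the overall F test** (nominal 5%, N = 88, simulation of the Aim 3 model including the interaction):

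| ρ within 65-80 | Ages 65-80, no age term | Ages 50-80, no age term | Age in the model |
|---|---|---|---|
| 0.1 | 5% | 6% | about 4-6% |
| 0.2 | 7% | 27% | about 4-6% |
| 0.3 | 14% | 84% | about 4-6% |

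Putting the R² values of step 4 into the noncentral F of step 1 agrees: for ages 50-80 it gives 28% at ρ = 0.2 (λ = 3.26) and 84% at ρ = 0.3 (λ = 12.6).

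**6. What each remedy does.** A floor of 65 alone leaves 14% at ρ = 0.3. The age term brings the rate back to about 5% whichever age range applies.

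**The case against.** The best defence is that the plan already points to an older, randomised sample. Only older adults are pseudo-randomised, the aims concern older people (Aim 1: "changes in cerebral perfusion using arterial spin labeling in older Veterans"), and the comparison programme is meant for people of 65 and over. Aim 3 is sized at 88, which is 2 × 44, and uses pre and post sessions, so young adults need not enter it. Within 65-80 and with weak age correlations, the distortion is negligible. Confounding also needs an age-BOLD relation that does not run through CBF or CVR, and the documents give no figure for one.

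Most of this stands, and it rules out some stronger readings:
- A reader might infer from the 18-to-80 range that young adults can be placed in an intervention arm. Section 6 does not allow that; the uncertainty concerns middle-aged volunteers.
- A reader might calculate the distortion for an Aim 3 sample spread over 18-80. Nothing in the documents describes such a sample.
- A reader might conclude that young adults take places from the 134. The two sections describe that total differently, but neither says young adults are counted in it.
- A reader might take 65 as the intended eligibility bound. It is a mailing filter and a programme descriptor.
- A reader might extend the concern to Aims 1 and 2. Age does not bias those randomised contrasts in expectation.

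What the defence does not answer is that the Aim 3 analysis set is only implied, 'older' has no number, and the model omits a variable that the plan itself links to both predictors.

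**Conclusion.** The concern holds for Aim 3. Leaving age out lets it create or inflate the association of CBF and CVR with task BOLD, and the open lower age limit widens the exposure. The size is not known from the documents. Under the assumptions above it runs from nothing detectable (ρ = 0.1, ages 65-80) to a test that nearly always rejects and an age-driven R² above the plan's benchmark (ρ = 0.3, ages 50-80). The middle case, ρ = 0.2, barely matters at 65-80 but raises the false-positive rate more than fivefold at 50-80. This is a possible bias of uncertain size, not a demonstrated error. It deserves correction because the remedy is cheap and works at every age range examined.

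**What to change.** 1. Add baseline age as a covariate in the Aim 3 regression, and report the increase in R² from CBF, CVR and their interaction over a model with age alone.
2. State that Aim 3 uses the randomised older participants only.
3. Give the lower age for the randomised cohort in Inclusion/Exclusion Criteria. Sixty-five is the only threshold the document already uses for recruitment and the comparison programme, but the sponsor may justify another.
4. Reconcile Sections 4 and 6 and the eligibility text on the young MRI comparison group: its age range, its size, its use, and whether it counts within the 134.

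**Cost.** Age is already named as a covariate for Aims 1 and 2, so no new data are needed. The age term uses one degree of freedom: power for the plan's 0.111, taken as a partial R², goes from 0.7828 to 0.7825. If age shares variance with CBF and CVR, the reported increase in R² will be smaller, which is the correct answer to the Aim 3 question. An age floor removes some volunteers below it; the documents do not show how many.
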